8.4.1. Serum Chemistry, Hematology, Coagulation, and Urinalysis

Clinical laboratory tests (serum chemistry, hematology and coagulation, urinalysis) will be performed at the time points detailed in [Table 1](#) and [Table 2](#). They may also be performed at any other time if clinically indicated. Clinical laboratory tests will be performed using the central

laboratory (refer to Section 8.4 for exceptions during the screening period). Specific laboratory tests to be performed are provided in [Table 9](#).

8.4.2. Other Clinical Laboratory Tests

At screening, patients will be tested for HIV, hepatitis B surface antigen, and hepatitis C antibody. At screening, visit 11, and ET and EOT visits, patients will be tested for thyroid stimulating hormone, triiodothyronine, and thyroxine.

8.4.2.1. Human Chorionic Gonadotropin and Follicle-Stimulating Hormone Tests

A serum β -HCG test will be performed for all women of childbearing potential at screening and the FU visit (see [Table 1](#) and [Table 2](#)). Urine β -HCG (dipstick) test will be performed for women of childbearing potential at all visits where study drug is administered (prior to study drug administration) and at the ET and EOT visits. A negative result must be obtained prior to study drug administration (if a borderline result is obtained on a urine test, a serum test should be performed and a negative result obtained prior to IMP administration).

Postmenopausal women (no menses for at least 12 months [without an alternative medical cause] prior to screening and with follicle-stimulating hormone (FSH) concentration above 35 U/L) may be allowed not to use contraceptives during the study. An FSH test will be performed at the screening visit for any female who has been without menses for at least 12 months prior to screening to confirm postmenopausal status.

8.4.2.2. Urine Drug Screen

A urine drug screen will be performed at the time points specified in [Table 1](#) and [Table 2](#). The urine drug screen detects the presence of drugs of abuse, including amphetamine, barbiturates, benzodiazepines, cocaine, opiates, and tetrahydrocannabinol.

Substance use disorder is exclusionary and will preclude the patient from randomization. However, if per the investigator's judgment, a patient does not meet the criteria for substance use disorder, a positive result for any of the above drugs or their metabolites is not exclusionary. Patients' eligibility in such case of positive result, without medical explanation, will be determined by the investigator based on the patient's background, history of substance use, and the investigator's discussions with family members, caregivers, or healthcare professionals, as applicable. The patients should be advised that use of these substances should be avoided during the study.

8.4.2.3. Prolactin

Blood samples will be obtained for prolactin test at the time points specified in [Table 1](#) and [Table 2](#) (at screening [prior to intake of oral olanzapine, where relevant], baseline [visit 2; week 0 (prior to IMP administration)], visit 11 [week 8 (prior to IMP administration)], visit 14 [week 20 (prior to IMP administration)], and at the EOT visit). As prolactin levels are highly affected by olanzapine and reach steady state approximately 8 weeks after treatment initiation ([Yang et al 2018](#)), in order to maintain the blind, prolactin level results obtained after first IMP administration and before visit 13 (8 weeks into Period 2) will not be available for review by the sponsor or the sites until Period 1 database lock. The IDMC will review the unblinded data periodically.

8.5. Physical Examinations

Physical examinations, including height (to be obtained at the screening visit only) and weight, will be performed at the time points detailed in [Table 1](#) and [Table 2](#). Full physical examination will be conducted at the screening visit and unscheduled visits only; the rest of the visits will include an abbreviated physical examination (including weight). The full physical examination will consist of examining the following body systems: cardiovascular, respiratory, abdominal, skin, neurological, and musculoskeletal systems. The physical examination will also include examination of general appearance, including head, eyes, ears, nose, and throat; chest; abdomen; skin; lymph nodes; and extremities. An abbreviated physical examination (general appearance, head, eyes, ears, nose, throat, lung, heart, skin, and extremities) will be conducted at the other time points and will include a brief neurological examination that includes examination of a subset of cranial nerves controlling vision and motor examination of a subset of larger muscle groups, including an assessment of muscle tone, reflexes, gait, and involuntary movements.

Any physical examination finding that is judged by the investigator as clinically significant (except at the screening visit) will be considered an adverse event, recorded on the CRF, and monitored as described in Section [8.1.2](#).

8.6. Vital Signs

Vital signs (blood pressure [systolic/diastolic], pulse and orthostatic changes, respiratory rate, and temperature) should be measured at each in-clinic visit pre-injection.

Vital signs should also be measured in the event of an injection site pus-containing lesion (abscess, infection, or inflammation), ulceration, or necrosis ([Table 1](#) and [Table 2](#)). All vital signs results outside of the reference ranges will be judged by the investigator as belonging to one of the following categories:

- abnormal and not clinically significant
- abnormal and clinically significant

Before blood pressure and pulse are measured, the patient must rest in a supine or semi-erect position for at least 5 minutes; measurements should be taken again after standing for approximately 2 minutes. (The same position and arm should be used each time vital signs are measured for a given patient.) For any abnormal vital sign value, the measurement should be repeated as soon as possible. Any vital sign value that is assessed by the investigator as clinically significant will be recorded both on the source documentation and the CRF as an adverse event, and monitored as described in Section [8.1.2](#).

8.7. Electrocardiography

A 12-lead ECG will be recorded at the time points detailed in [Table 1](#) and [Table 2](#). At screening and baseline, measurements will be done in triplicate (approximately 5 minutes apart). Single measurements will be performed at all other in-clinic visits where ECG recordings are taken. All ECG recordings should be sent to the central diagnostic center at screening, baseline, and throughout the study. A qualified physician at a central diagnostic center will interpret the ECG.

Patients' eligibility at screening may be determined based on the investigator or designee ECG interpretation.

[figure not shown]
In case only local ECGs interpretations are available within the screening period and they indicate that the patient is eligible for randomization, the patient may be randomized (provided all other study eligibility criteria are met). When central diagnostic ECG interpretation becomes available (after randomization), the patient's eligibility should be re-confirmed. In case the central diagnostic interpretation suggest that the patient does not meet study eligibility criteria, it is recommended to repeat the ECG and consult the MM.

All ECG results outside of the reference ranges will be judged by the investigator as belonging to one of the following categories:

- abnormal and not clinically significant
- abnormal and clinically significant

Any ECG finding that is assessed by the investigator as clinically significant (except at the screening visit) will be considered an adverse event, recorded on the source documentation and in the CRF, and monitored as described in Section 8.1.2.

8.8. Assessment of Local Tolerability and Pain

Test	Response
[REDACTED]	[REDACTED] [REDACTED] [REDACTED] [REDACTED]
[REDACTED]	[REDACTED] [REDACTED] [REDACTED]
[REDACTED]	[REDACTED]
[REDACTED] [REDACTED] [REDACTED]	[REDACTED] [REDACTED] [REDACTED]
[REDACTED]	[REDACTED] [REDACTED] [REDACTED] [REDACTED]

[figure not shown]
8.8.1. Procedures for Injection Site Pus-Containing Lesion (Abscess, Infection, or Inflammation), Ulceration, Necrosis, or Atrophy

8.9. Assessment of Suicidality

The C-SSRS will be used to assess the patient's suicidal ideation (severity and intensity) and behavior (Posner et al 2011). The C-SSRS Baseline/Screening version will be administered by a qualified HCP (ie, the investigator or a qualified person designated by the investigator) at screening, and the C-SSRS Since Last Visit version will be completed at all other time points, as described in [Table 1](#) and [Table 2](#). Following any positive finding on the C-SSRS Since Last Visit version, the patient must be evaluated by the Principal Investigator or a patient's mental health practitioner designated by the investigator, which may result in the patient's withdrawal from the study. Recording of positive findings as adverse events will be per investigator decision.

8.10. Post-injection Delirium/Sedation Syndrome Monitoring

Term	Percentage (%)
GDP	98
Inflation	95
Interest rates	95
Central bank	95
Monetary policy	95
Quantitative easing	95
Inflation targeting	95
Interest rate hike	95
Interest rate cut	95
Interest rate parity	60
Nominal interest rate	50
Real interest rate	50

8.11. Other Safety Assessments

8.11.1. Abnormal Involuntary Movement Scale

The AIMS will be performed at the time points specified in [Table 1](#) and [Table 2](#). The AIMS scores the occurrence of tardive dyskinesia in patients receiving neuroleptic medications ([Guy 1976a](#)). The AIMS is a 14-item scale that includes assessments of orofacial movements,

extremity and truncal dyskinesia, examiner's judgment of global severity, subjective measures of awareness of movements and distress, and a yes/no assessment of problems concerning teeth and/or dentures. Higher scores indicate greater severity of the condition.

8.11.2. Barnes Akathisia Rating Scale

The BARS will be performed at the time points specified in [Table 1](#) and [Table 2](#). The BARS is an instrument that assesses the severity of drug-induced akathisia ([Barnes 1989](#)). The BARS includes 3 items for rating objective restless movements, subjective restlessness, and any subjective distress associated with akathisia that are scored on a 4-point scale of 0 to 3 and summed, yielding a total score ranging from 0 to 9. The BARS also includes a global clinical assessment of severity scored on a scale of 0 to 5. Higher scores are indicative of greater severity of akathisia.

8.11.3. Simpson-Angus Scale

The SAS will be performed at the time points specified in [Table 1](#) and [Table 2](#). The SAS is a 10-item instrument for the assessment of neuroleptic-induced parkinsonism ([Simpson and Angus 1970](#)). The items on the scale include measurements of hypokinesia, rigidity, glabellar reflex, tremor, and salivation. Each item is rated on a 5-point scale (0 to 4), with a higher score indicating greater severity of symptoms. The mean score is calculated by adding the individual item scores and dividing by 10.

8.11.4. Calgary Depression Scale for Schizophrenia

The CDSS will be performed at the time points specified in [Table 1](#) and [Table 2](#). The CDSS is specifically designed to assess the level of depression separate from the positive, negative, and extrapyramidal symptoms in schizophrenia ([Addington et al 1993](#)). This clinician-administered instrument consists of 9 items, each rated on a 4-point scale from 0 (absent) to 3 (severe).

9. ASSESSMENT OF PHARMACOKINETICS/PHARMACODYNAMICS/BIOMARKERS/PHARMACOGENETICS

9.1. Pharmacokinetic Assessment

[figure not shown]
Blood volumes are provided in the ICF and laboratory manual. Details on sample handling, storage, shipment, and analysis are provided in the laboratory manual.

9.2. Pharmacodynamic Assessment

A horizontal bar chart consisting of four solid black bars of increasing length from left to right. The bars are separated by small gaps and are set against a white background.

9.3. Assessment of Exploratory Biomarkers

Term	Percentage
GDP	98
Inflation	97
Interest rates	95
Central bank	94
Monetary policy	93
Quantitative easing	92
Inflation targeting	91
Central bank independence	89

9.4. Pharmacogenetics

For information regarding pharmacogenetic assessments, see [Appendix H](#).

9.5.

10. STATISTICS

This section describes the statistical analysis as foreseen at the time of planning the study. Changes, additions, and further details about the analyses will be described in the statistical analysis plan. After finalization of the statistical analysis plan and unblinding of Period 1, any additional analyses or changes to analyses that may be required will be fully disclosed in the clinical study report (CSR). In the event of any contradiction between the study protocol and the statistical analysis plan, the statistical analysis plan will prevail.

The primary endpoint is change from baseline to week 8 in the PANSS total score. The sample size is designed to detect with [REDACTED] probability a standardized mean difference of [REDACTED] (eg, an improvement of at least [REDACTED] points in the PANSS total score, assuming a standard deviation of [REDACTED] points). The 3 primary efficacy hypotheses will be tested with an overall type I error of 0.05, controlled using truncated Hochberg adjustment for multiplicity.

10.1. Sample Size and Power Considerations

The following assumptions are made for the sample size determination:

1. Standardized mean difference of [REDACTED]
2. Homogenous variance
3. Overall 2-sided alpha of 0.05
4. Power of [REDACTED]
5. Randomization ratio of 1:1:1:1
6. Truncated Hochberg adjustment for multiplicity

For the sample size calculation, a 2-sample t-test and a [REDACTED] correction (ie, 2-sided alpha of [REDACTED]) were used, which yielded a conservative sample size. A simulation study with the above assumptions was conducted to evaluate the power using mixed-model repeated measures (MMRM) with truncated Hochberg as a multiplicity control method; the power to demonstrate statistically significant superiority in the 3 active treatment groups versus placebo for the primary endpoint was about [REDACTED].

Approximately 440 patients completing week 8 are needed to achieve the above power, per a comparison. Despite the fact that missing data after discontinuation will be imputed, for simplicity, it is assumed that the ET rate in Period 1 will be [REDACTED], and the overall sample size is adjusted for that; hence, the number of patients to be randomized is approximately 640.

Once 440 patients complete week 8 in Period 1, randomization to placebo may be stopped, and new patients will then be randomized to the active treatment groups only (Section 6.9.3). The efficacy analysis will include all patients randomized until the time point at which randomization to placebo was stopped. Patients randomized after the randomization to placebo group was stopped will not be included in the efficacy analyses.

10.2. Analysis Sets

10.2.1. Full Analysis Set

The full analysis set will include all patients randomized to Period 1 regardless of the actual treatment the patients received.

10.2.2. Efficacy Analysis Set

The efficacy analysis set will include all patients randomized to Period 1 while patients are randomized to 1 of the 3 TV-44749 doses or placebo, regardless of the actual treatment the patients received.

Patients randomized after randomization to the placebo group is stopped (Section 10.1) will not be included in the efficacy analysis set.

This analysis set will be used for the primary efficacy estimand.

10.2.3. Safety Analysis Set

To address the safety objective by the safety estimand, the safety analysis set will include all randomized patients who received at least 1 dose of TV-44749 olanzapine or placebo.

In the safety analysis set, treatment will be assigned based on the treatment patients actually received, regardless of the treatment to which they were randomized, unless otherwise specified.

In cases of dosing error, treatment assignment of these patients will be decided in a blinded manner prior to unblinding of Period 1 and will be documented in the study data review document.

10.2.4. Pharmacokinetic Analysis Set

The pharmacokinetic analysis set will include those patients from the safety analysis set who have ≥ 1 plasma concentration measured.

10.3. Data Handling Conventions

Detailed data imputation rules will be described in the statistical analysis plan.

10.3.1. Handling Withdrawals and Missing Data

10.4. Study Population

The full analysis set (Section 10.2.1) will be used for all study population summaries, unless otherwise specified. Summaries will be presented by treatment group and study period for all patients.

10.4.1. Patient Disposition

Data from patients screened, patients screened but not randomized and reason for not randomized, patients who are randomized (full analysis set), patients randomized but not treated and reason, randomized and dosed (safety analysis set), and all other analysis sets, patients who complete the study, and patients who either discontinue IMP or withdraw from the study, will be summarized using descriptive statistics. Data from patients who discontinue IMP or withdraw from the study will also be summarized by reason for withdrawal using descriptive statistics.

10.4.2. Demographic and Baseline Characteristics

Patient demographic and baseline characteristics, including medical history, prior medications and therapies, and ECG findings, will be summarized using descriptive statistics by full analysis set and safety analysis set. For continuous variables, descriptive statistics (number [n], mean, standard deviation, median, minimum, and maximum) will be provided. For categorical variables, patient counts and percentages will be provided. Categories for missing data will be presented if necessary.

10.5. Efficacy Analysis

10.5.1. Primary Estimand

Refer to Section 3.2.1 for a description of the primary estimand.

10.5.2. Primary Endpoint

The primary efficacy endpoint is the change from baseline to week 8 in the PANSS total score.

10.5.3. Other Estimands

Refer to Section 3.2.2 for a description of the other efficacy estimand.

Refer to Section 3.2.3 for a description of the safety and tolerability estimand.

10.5.4. Secondary Endpoints

Secondary endpoints are listed in Section 3.1.

10.5.5. Exploratory Endpoints

Exploratory endpoints are listed in Section 3.3.

10.5.6. Planned Method of Analysis

The efficacy analysis set (Section 10.2.1) will be used for all efficacy analyses. Summaries will be presented by treatment group and study period, but only data from Period 1 will be considered for efficacy purposes.

10.5.6.1. Primary Efficacy Analysis

[figure not shown]
The efficacy analysis will employ multiple imputation, MMRM, and Rubin's rule.

1. One hundred completed datasets will be imputed using multiple imputation.

- a. For ICEs of a use of prohibited antipsychotic medication or early discontinuation due to insufficient clinical response, imputations will be done assuming MNAR in order to estimate what would have happened if patients who discontinued early had remained in the study on placebo treatment.
- b. For ICEs of early discontinuation due to a reason that is not lack of efficacy or death, a multiple imputation assuming that the clinical effect in these patients is similar to those not experiencing ICE during the study (ie. assuming MAR) will be employed. Full details of the methods employed for the 2 types of ICEs and underlining assumptions will be detailed in the statistical analysis plan.

2. MMRM on change from baseline to week 8: least squares means of change from baseline to week 8, for each of the 4 treatment arms and for the differences between each of the TV-44749 arms to placebo, 95% confidence interval, and p-values will be calculated using MMRM analysis for each complete dataset. The model will include treatment arm, study visit, treatment-visit interaction, stratification variables, and PANSS total score at baseline as covariates. Unless otherwise specified, unstructured covariance matrix will be used as a covariance matrix. Further details about the analysis will be presented in the statistical analysis plan.
3. Summary statistics for the primary efficacy endpoint will be based on Rubin's rule summary of least squares means of change from baseline to week 8, for each of the 4 treatment arms and for the differences between each of the TV-44749 arms to placebo, 95% confidence interval, and p-values. The Rubin's-derived p-values that will be adjusted according to truncated Hochberg method (Section 10.6) will be used for the primary efficacy analysis.

10.5.6.2. Sensitivity Analysis

10.5.6.3. Supplementary Analysis

The primary and key secondary endpoints will be repeated using treatment policy estimand (ie, intention to treat). The treatment policy estimand will be defined as:

- a. **Treatment:** The treatment of low, medium, or high dose of TV-44749 compared to placebo, separately, will be evaluated according to the randomization assignment at Period 1.
- b. **Population:** All randomized adult patients who have a confirmed diagnosis of schizophrenia, present with acute exacerbation of disease, and are eligible for olanzapine treatment.

- c. **Endpoint:** Change from baseline to week 8 in the PANSS total score, regardless of the ICEs patients experienced during Period 1.
- d. **Population-level summary:** Least squares means of the difference in the change from baseline to week 8 between treatment groups according to the randomization assignment, regardless of the treatment actually received.

Assuming that missing data generated in the study, such as ET, follow the MAR assumption, this analysis complies with estimation of the mean treatment effect comprised with the intention to treat principle.

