In the case of patients lost to follow-up, attempts to contact the patient must be made and documented in the patient’s medical records and transcribed to the CRF.

Randomized patients who meet 1 or more of the study discontinuation or withdrawal criteria should be invited to perform the ET visit as soon as possible. An EOT visit will be conducted at 4 weeks after the last dose of IMP, and a FU visit for safety evaluation will be conducted at 8 weeks after the last dose of IMP. In case the ET visit is conducted during the time window of the EOT visit, the ET and EOT visits may be conducted on the same day (ie, the visits will be combined, and all assessments listed in the Study Procedures and Assessments tables [[Table 1](#) or [Table 2](#)] for the ET and EOT visits must be performed). Patients who discontinue study treatment should be encouraged to complete the remaining visits until completion of the study (ie, ET, EOT, and FU visits).

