1.2.3. Estimand Using the Treatment Policy Strategy

As supplementary analyses (Section 10.5.6.3 in the Protocol), the primary and key secondary objectives will be evaluated where all ICEs are handled using the Treatment Policy strategy (i.e., all available data will be analyzed regardless of ICE). *The estimand attributes for treatment, population, endpoint and population-level summary will be the same as described in the Primary Estimand and Key Secondary Efficacy Estimand sections*, respectively. This estimand addresses the following clinical question of interest: "What is the treatment benefit of a patient regardless of treatment adherence or early discontinuation over 8 weeks?".

In addition to the primary and key secondary endpoints, the other secondary efficacy endpoints in Period 1 will also be analyzed according to this estimand: PANSS, CGI-I, CGI-S, PGI-I, SQLS, PSP, and [REDACTED] (Section 6.4 and Appendix D).

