4.3. Handling Withdrawals and Missing Data

Despite the best efforts to obtain complete data, missing data is unavoidable. Unless otherwise specified, only observed patient data will be used in the statistical analyses.

According to the definition of the primary efficacy estimand, it is planned to assign multiple possible values to each missing efficacy data point (i.e., missing primary and secondary efficacy endpoints) by employing multiple imputation methodology (see Section 4.3.1 and Section 6.2.2), in addition a multiple imputation procedure is planned to assess the robustness of the underlying assumption for the primary efficacy analysis using the tipping point approach (see Section 17 and [Appendix A](#) below).

Ad-hoc imputation for safety summary tables will be performed only for the specific cases described below. There will be no imputation in the data listings (including ad-hoc imputation); all values will be displayed as recorded in the clinical database. No imputation will be performed for missing items in efficacy and safety scales.

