6.2.3. Multiple Imputation Methods

For ICEs using the hypothetical strategy (Section 1.2.1), data collected after the ICE will be handled as analysis missing, and a multiple imputation method will be used to handle this missing data.

For ICEs of early discontinuation of randomized treatment due to lack of efficacy/disease progression, or use of prohibited antipsychotic medication that are not part of the management of patients with schizophrenia (see Section 1.2.1), imputations will be performed assuming Copy Increment from Reference (CIR) in order to estimate what would have happened if patients who discontinued early had remained in the study and had a similar ('trend') slope to patients on placebo group from the time of ICE onward (White et al 2019).

For ICEs of early discontinuation of randomized treatment due to a reason that is not lack of efficacy, imputations will be performed using MAR, i.e., assuming that the clinical effect in these patients is similar to those in the same treatment arm that did not experience an ICE during the study.

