6.3.2.2. Analysis

Analysis will be conducted following the same steps as described in Section [6.2.4](#) except that the outcome variable will instead be the PSP score.

6.3.3. PANSS Total Score – Change From Baseline to Weeks 1, 2, 4 and 8

By visit analysis of change from baseline will be conducted based on the treatment policy, in addition to the by visit analyses based on the primary efficacy estimand. A mixed model repeated measures (MMRM) analysis will be performed using the PANSS total score and change in PANSS total score from baseline as the dependent variable, and treatment arm, study visit, treatment-visit interaction, stratification variables (sex and geographic region), age, and PANSS total score at baseline (only for the change from baseline model) as covariates. An unstructured covariance matrix will be used in all models. Analyses will be performed in SAS using the Kenward-Roger option to estimate the denominator degrees of freedom and standard errors.

6.3.4. Clinical Global Impression-Improvement (CGI-I) scale – At Weeks 4 and 8

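### The supplementary treatment policy analysis relies on MAR after early termination, so it can overstate the effect through patients who miss the Week 4 injection

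*Protocol*

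**What the plan says.** - **Protocol 10.5.6.3** repeats the primary and key secondary analyses under a treatment policy estimand that ignores intercurrent events (ICEs). It justifies this as intention to treat: "Assuming that missing data generated in the study, such as ET, follow the MAR assumption, this analysis complies with estimation of the mean treatment effect".
- **SAP 1.2.3** takes this over, citing that Protocol section. Its question is "What is the treatment benefit of a patient regardless of treatment adherence or early discontinuation over 8 weeks". Its rule for observed data is that "all available data will be analyzed regardless of ICE". No readable rule covers data that are absent.
- **SAP 4.3** gives the default: "Unless otherwise specified, only observed patient data will be used in the statistical analyses". Multiple imputation is tied there to the primary estimand.
- **SAP 6.3.3** gives the PANSS model: "By visit analysis of change from baseline will be conducted based on the treatment policy, in addition to the by visit analyses based on the" (the sentence closes by naming the main estimand). It is an MMRM with arm, visit, their interaction, sex, region, age and baseline. It has no term for on or off treatment.
- **Protocol 5.4**, on visits after stopping: "Patients who discontinue study treatment should be encouraged to complete the remaining visits until completion of the study (ie, ET, EOT, and FU visits". EOT falls 4 weeks after the last dose and FU 8 weeks after it. PANSS, CGI-S and PSP are collected at ET, EOT and FU (Protocol Table 1, Appendix B).
- **SAP 4.4** moves an ET or EOT result to a scheduled visit if it falls in that visit's window and the scheduled result is missing. FU is not named, and unscheduled visits are not mapped.
- **SAP 6.3.8** sets PSP after withdrawal from treatment to missing and reports Weeks 4 and 8 from that model. SAP 1.2.3 lists PSP among the treatment policy endpoints.
- On precedence, Protocol 10 says: "In the event of any contradiction between the study protocol and the statistical analysis plan, the statistical analysis plan will prevail". SAP 1.2.3 does not contradict the MAR sentence, so the sentence stands.

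**The concern.** A treatment policy effect includes what happens to patients after they stop. An MMRM on available data handles an absent Week 8 score under MAR: it predicts the score from the patient's earlier values and from same-arm patients who have later values, most of whom stayed on treatment. SAP 6.2.3 describes MAR imputation in these terms, as "assuming that the clinical effect in these patients is similar to those in the same treatment arm that did not experience an ICE during the" trial. That text is written for the primary estimand, where data after an ICE are removed, but it also describes what the MMRM does with a score that was never collected or never mapped. For such patients the analysis comes close to Sensitivity Analysis #1 (SAP 6.2.5.1), although SAP Appendix D lists the two as separate strategies.

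The label carries weight. SAP Amendment 01 introduced this estimand and gives a regulator's comments as the reason. Protocol 6.9.4 says that an arm failing the topline analysis might still be submitted on all the evidence, including secondary endpoints and sensitivity analyses. A result labelled intention to treat would be used in that argument.

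**Working it through.** **1. Early termination rate.** The rate is blacked out, so it can only be inferred from the sample size (Protocol 10.1, SAP 2.5): 440 completers, 640 randomized. From 440/(1 − d) = 640, d = 1 − 440/640 = 31.25%. Nearby rates give 440/0.70 = 629 and 440/0.67 = 657, so roughly 30-33% fits. The 440 cannot be reproduced, because the effect size, power and corrected alpha are also blacked out.

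**2. Who is affected.** Period 1 has two injections, at Weeks 0 and 4 (Protocol 4.1).
- Stop after the second injection: EOT is due at 4 + 4 = Week 8, and SAP 4.4 maps it if it falls in the window. The patient has had all Period 1 drug and is within the 4 weeks after dosing for which the Protocol says further antipsychotic treatment is not required unless clinically indicated.
- Stop after the first injection only: EOT is due at 0 + 4 = Week 4 and FU at 0 + 8 = Week 8. FU includes PANSS, but SAP 4.4 does not map it.

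The mismatch therefore lies mainly with the second group.

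**3. Size if loss of drug benefit is the only mechanism.** Let d be the share stopping, q the share of stoppers who miss the Week 4 injection, and L the share of benefit they lose by Week 8. Assume equal dropout across arms, no change in placebo stoppers, and later stoppers still covered. Then:

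treatment policy effect / MAR estimate = 1 − d·q·L

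| q | L | Ratio | MAR overstates by |
|---|---|---|---|
| 0.5 | 0 | 1.000 | 0% |
| 0.5 | 0.5 | 1 − 0.3125×0.25 = 0.922 | 1/0.922 − 1 = 8.5% |
| 0.5 | 1 | 1 − 0.3125×0.5 = 0.844 | 18.5% |
| 1 | 1 | 1 − 0.3125 = 0.688 | 45.5% |

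The documents give neither q nor L; both are assumptions.

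**4. Simulation check.** 200,000 per arm, eight weekly visits, correlation 0.85 between adjacent visits, assumed on-drug effect 0.5 SD, 31.25% dropout, maximum likelihood under MAR within arm.

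| Scenario | MAR estimate (SD) | True treatment policy (SD) | Ratio |
|---|---|---|---|
| Half miss Week 4, no loss | −0.499 | −0.500 | 1.00 |
| Half miss Week 4, half lost | −0.498 | −0.459 | 1.09 |
| Half miss Week 4, all lost | −0.506 | −0.426 | 1.19 |
| As above, 80% of later stoppers' EOT mapped | −0.495 | −0.416 | 1.19 |
| All miss Week 4, all lost | −0.501 | −0.347 | 1.44 |
| Half miss, all lost; stoppers in both arms gain 0.5 SD from other antipsychotics | −0.501 | −0.422 | 1.19 |
| Half miss, all lost; only placebo stoppers gain 0.5 SD | −0.504 | −0.267 | 1.89 |
| Half miss, all lost; only active stoppers gain 0.5 SD | −0.503 | −0.580 | 0.87 |

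Mapping the later stoppers' EOT leaves the ratio at 1.19, because the bias comes from early stoppers. Mapping FU was not simulated.

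**The case against.** The case on the other side is substantial.

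- **Two-injection design.** Patients who stop after Week 4 have a completer's Period 1 exposure, and their EOT can supply Week 8. This stands, and it confines the point to those who miss the second injection.
- **Observed data after an ICE are kept.** This stands. A reader might infer that every score after stopping is replaced by an on-drug prediction; SAP 1.2.3 says otherwise.
- **The Protocol sentence is conditional.** If data were MAR given everything observed, the model would be consistent for the treatment policy mean. This stands as logic. But few off-treatment Week 8 values enter the model and no term separates on from off treatment, so the condition is hard to defend for early stoppers.
- **Silence and redaction.** A reader might infer that the SAP rules out imputation for treatment policy PANSS. It does not: an explicit bar on multiple imputation appears only for SQLS (6.3.7.2) and in 6.3.8 for PSP. SAP 6.3 refers secondary endpoints to the methods of 6.2, and SAP 4.3.1 and much of Appendix B are blacked out. Further detail may exist there.
- **Not the only such analysis.** The modified treatment policy estimand (SAP 1.2.4) also disregards early discontinuation. It discards data after antipsychotic use and gives no readable missing-data rule, so it does not fill the gap.
- **It is supplementary.** This stands. The primary analysis uses copy-increments imputation for lack-of-efficacy stoppers and has its own tipping-point analysis (SAP 6.2.5.2).

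**Conclusion.** The point holds for patients who stop before the Week 4 injection. For them the supplementary analysis approaches the all-MAR sensitivity analysis and can overstate the treatment policy effect. At the implied 31% early termination, with half of stoppers assumed to miss the second injection, the overstatement is about 8-9% if half the benefit is lost and 19% if all is lost.

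Two stronger readings are tempting. One is that the effect will be overstated by about 45%. That needs every stopper to miss the second injection, lose all benefit and contribute no Week 8 score; it is the extreme bound for loss of benefit alone. The other is that overstatement is certain. It is zero if no benefit is lost, and it reverses (ratio 0.87) if active-arm stoppers gain more from later antipsychotics; it grows (1.89) if only placebo stoppers gain. The documents fix neither the share stopping early nor what those patients take next.

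The primary result is unaffected. The change should still be made, because the stated approach can give a biased answer to the plan's own question.

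**What to change.** 1. **SAP 4.4:** for the treatment policy analysis, map EOT or FU PANSS, CGI-S and PSP that fall in the Week 8 window to Week 8. The Week 8 dosing-visit window is ±3 days, while EOT allows ±1 week and FU −1/+2 weeks, so some values will stay unmapped.
2. **SAP 1.2.3:** keep MAR only for gaps while on treatment. Impute values still missing after discontinuation from same-arm retrieved dropouts with the same number of injections. Pooling all retrieved dropouts would mostly give early stoppers the scores of later, still-covered patients. Where matching donors are too few, use the reference-based (CIR) imputation already planned for the primary analysis.
3. **Protocol 10.5.6.3:** replace the sentence equating MAR with intention to treat by this method.
4. **SAP 6.3.8:** reconcile the rule setting PSP to missing after treatment withdrawal with SAP 1.2.3. SAP 6.3.7.2 has the same rule for SQLS.

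Cost: wording and reuse of planned imputation methods, with no new patients or visits. The supplementary estimate may be smaller and its confidence interval wider.
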